#### **10.3.6 Blinding**

This is an open label study.

#### **10.3.7 Treatment Compliance**

Patients will be instructed to take study medication as directed and bring all IP containers and remaining test medication at each study visit. Patient compliance with the dosing regimen will be assessed by reconciliation of the used and unused IP. The quantity dispensed, returned, used, lost, etc., must be recorded on the medication dispensing log provided for the study.

#### **10.3.8 Investigational Product Accountability**

The Catalyst designee is responsible for maintaining accurate records (including dates and quantities) of IP received and sending IP to the site. The clinical site is responsible for maintaining accurate records for IP dispensed, returned, and IP lost or destroyed. The Investigator, study site coordinator or designee must retain all unused or expired study supplies until the study monitor (on-site CRA) has confirmed the accountability data.

#### **10.3.9 Return and Disposition of Clinical Supplies**

Unused IP must be kept in a secure location for accountability and reconciliation by the study monitor. The Investigator or designee must provide an explanation for any destroyed or missing IP or study materials.

	SMA-002	Page 25
---	---------	---------

Unused IP may be destroyed on site, per the site's standard operating procedures, but only after Catalyst has granted approval for drug destruction. The monitor must account for all IP in a formal reconciliation process prior to IP destruction. All IP destroyed on site must be documented. Documentation must be provided to Catalyst and retained in the Investigator study files. If the site is unable to destroy IP appropriately, the site can return unused IP to Catalyst upon request. The return of IP or IP materials must be accounted for on a Study Drug Return Form provided by Catalyst.

All IP and related materials should be stored, inventoried, reconciled, and destroyed or returned according to applicable regulations and study procedures.

#### **10.4 Prior and Concomitant Medications**

All prescription and over-the-counter medications and herbal and nutritional supplements taken during the Long-Term study will be recorded on the designated CRF. All prior medications taken within 14 days of initiation of this study are to be recorded on the CRF which is also recorded in the appropriate CRF pages of Study SMA-001 as concomitant medication.

The Investigator may prescribe additional medications during the study, if the prescribed medication is not prohibited by the protocol. In the event of an emergency, any needed medications may be prescribed without prior approval, but the medical monitor must be notified of the use of any contraindicated medications immediately thereafter. Any concomitant medications added or discontinued during the study should be recorded on the CRF.

Medications that are contraindicated when combined with amifampridine phosphate are:

- Medicinal products with narrow therapeutic window
- Sultopride

Amifampridine phosphate should be used with caution when combined with the following products:

- Medicinal products known to lower the epileptic threshold
- Medicinal products with atropinic effects
- Medicinal products with cholinergic effects
- Non depolarizing muscle relaxant acting medicinal products

	SMA-002	Page 26
---	---------	---------

- Depolarizing muscle relaxant acting medicinal products.

## 10.5 Dietary or Other Protocol Restrictions

### 10.5.1 Dietary Restrictions

There are no dietary restrictions for patients during any part of this study.

### 10.5.2 Contraception

Sexually active males and females of childbearing potential and their partners must use effective forms of contraception, including: combined hormonal contraception associated with inhibition of ovulation (oral, intravaginal, transdermal); progestogen-only hormonal contraception associated with inhibition of ovulation (oral, injectable or implantable); intrauterine device; intrauterine hormone-releasing system; bilateral tubal occlusion; vasectomised partner; sexual abstinence.

According to CTFG guidelines a woman is considered of childbearing potential, i.e. fertile, following menarche and until becoming post-menopausal unless permanently sterile. Permanent sterilisation methods include hysterectomy, bilateral salpingectomy and bilateral oophorectomy.

A postmenopausal state is defined as no menses for 12 months without an alternative medical cause.

## 10.6 Safety Variables

Safety in this study will be determined from evaluation of AEs/SAEs, vital signs assessments, clinical laboratory assessments, ECGs, and physical examinations. Pregnancy testing is also required for females of childbearing potential. The timing of the required evaluations is described in the Schedule of Events in [Table 1](#) and in Section 13.

### 10.6.1 Adverse Events

The determination, evaluation and reporting of AEs will be performed as outlined in Section 11.

### 10.6.2 Vital Signs

Specific visits for obtaining vital signs are provided in Table 1 and in Section 13. Vital signs will be measured while in a sitting position, after resting for 5 minutes, and include SBP and DBP measured in millimeters of mercury (mmHg), heart rate in beats per minute, respiration

	SMA-002	Page 27
---	---------	---------

rate in breaths per minute. Weight (kg) and temperature in degrees C will also be measured. Clinically significant changes from baseline will be recorded as AEs.

#### **10.6.3 Clinical Laboratory Assessments**

Specific visits for obtaining clinical laboratory assessment samples are provided in [Table 1](#) for the tests required by Protocol. The scheduled clinical laboratory tests are listed in Table 2. In brief, clinical laboratory evaluations are to be performed every 3 to 6 months. These tests can be performed more frequently at the discretion of the Investigator.

All abnormal clinical laboratory result pages should be initialed and dated by an Investigator, along with a comment for each abnormal result indicating whether or not it is clinically significant. Any abnormal test results determined to be clinically significant by the Investigator should be repeated (at the Investigator's discretion) until the cause of the abnormality is determined, the value returns to baseline or to within normal limits, or the Investigator determines that the abnormal value is no longer clinically significant.

Each clinically significant laboratory result should be recorded as an AE. The diagnosis, if known, associated with abnormalities in clinical laboratory tests that are considered clinically significant by the Investigator will be recorded on the AE CRF.

**Table 2 Clinical Laboratory Tests**

Blood Chemistry	Hematology	Urine Tests	Other
Albumin	Hemoglobin	Appearance	Pregnancy test, if applicable
Alkaline phosphatase	Hematocrit	Color	
ALT (SGPT)	WBC count	pH	
AST (SGOT)	RBC count	Specific gravity	
Direct bilirubin	Platelet count	Ketones	
Total bilirubin	Differential cell count	Protein	
BUN		Glucose	
Calcium		Bilirubin	
Chloride		Nitrite	
Total cholesterol		Urobilinogen	
CO 2 or bicarbonate		Blood in urine	
Creatine phosphokinase			
Creatinine			
Glucose			
GGT			
LDH			
Phosphorus			
Potassium			
Total protein			
Sodium			
Uric acid			

ALT, alanine aminotransferase; AST, aspartate aminotransferase; BUN, blood urea nitrogen; CO2, carbon dioxide; GGT, gamma-glutamyl transferase; LDH, lactate dehydrogenase; RBC, red blood cell; SGOT, serum glutamic-oxaloacetic transaminase; SGPT, serum glutamic-pyruvic transaminase; WBC, white blood cell.

#### 10.6.4 Pregnancy Testing

Female patients of childbearing potential will have a urine pregnancy test at the end of the double-blind period on Day 10 and at other time points specified in the Schedule of Events (Table 1) and in Section 13. Female patients with a positive pregnancy test at end of the double-blind study are not eligible for enrollment. Additional pregnancy tests will be performed at any visit in which pregnancy status is in question.

Refer to Section 11.4 for details on the reporting procedures to follow in the event of pregnancy.

#### 10.6.5 Electrocardiogram (ECG)

A standard 12-lead safety ECG (single tracing) will be recorded with the patient resting comfortably in the supine position at the time points specified in the Schedule of Events

(Table 1) and in Section 13. Clinically significant changes from baseline will be recorded as AEs.

#### **10.6.6 Physical Examination**

A complete physical examination is to be performed at each clinic visit or, if applicable, at early discontinuation from the study. Complete physical examination will include assessments of general appearance as well as the following:

- Head
- Eyes
- Ears
- Nose
- Throat
- Cardiovascular
- Dermatologic
- Lymphatic
- Respiratory
- Gastrointestinal
- Musculoskeletal

Body weight will be measured with each physical examination throughout the study.

Other body systems may be examined. Clinically significant changes from baseline will be recorded as AEs.

#### **10.7 Efficacy Variables**

Every 3 or 6 months, each patient will be assessed with the QoL questionnaire.

##### **10.7.1 Quality of life assessment**

The Individualized Quality of Life for neuromuscular disease (INQoL) or the Pediatric Quality of Life (PEDSQL™) will be assessed for adult or pediatric patients, respectively. For the purposes of this study, the same QoL assessment instrument must be used throughout the study even if he/she becomes an adult. Each QoL evaluation is available in the local language for the appropriate sites.

## 11 REPORTING ADVERSE EVENTS

### 11.1 Adverse Events

For this protocol, a reportable AE is any untoward medical occurrence (e.g. sign, symptom, illness, disease or injury) in a patient administered the IP or other protocol-imposed intervention, regardless of attribution. This includes:

- AEs not previously observed in the patient, that emerge during the study.
- Pre-existing medical conditions judged by the Investigator to have worsened in severity or frequency or changed in character during the study.
- Complications that occur as a result of non-drug protocol-imposed interventions.

An adverse drug reaction is any AE for which there is a reasonable possibility that the IP caused the AE. “Reasonable possibility” means there is evidence to suggest a causal relationship between the IP and the AE.

Whenever possible, it is preferable to record a diagnosis as the AE term rather than a series of terms relating to a diagnosis.

All ongoing non-serious AEs, even those which began under Protocol SMA-001, will be reported from the end of the double-blind study (SMA-001) or from Day 0 for those not randomized to double blind medication in SMA-001 through the termination visit or at the early termination visit and will be recorded on the AE page of the eCRF. All ongoing SAEs from SMA-001 will be reported. The criteria for determining, and the reporting of new SAEs is provided in Section 11.2.

The Investigator should follow all unresolved AEs until the events are resolved or stabilized, the patient is lost to follow-up, or it has been determined that the study treatment or participation is not the cause of the AE. Resolution of AEs (with dates) should be documented on the appropriate CRF page(s) and in the patient’s medical record.

The Investigator responsible for the care of the patient or qualified designee will assess AEs for severity, relationship to IP, and seriousness (refer to Section 11.2 for SAE definition). Severity (as in mild, moderate or severe headache) is not equivalent to seriousness, which is based on patient/event outcome or action criteria usually associated with events that pose a threat to a patient’s life or functioning. Seriousness (not severity) serves as a guide for defining regulatory reporting obligations.

The Investigator will determine the severity of each AE using grades defined in Table 3 Categories of Severity of Adverse Events (the event will be recorded on the source documents and AE CRF). Events that are Grades 4 and 5 are serious events and require completion of both an SAE form and AE CRF.

**Table 3 Categories of Severity of Adverse Events**

Severity	Description	
Grade 1	Mild; asymptomatic or mild symptoms; clinical or diagnostic observations only; intervention not indicated.	
Grade 2	Moderate; minimal, local or noninvasive intervention indicated; limiting age-appropriate instrumental ADL*.	
Grade 3	Severe or medically significant but not immediately life-threatening; hospitalization or prolongation of hospitalization indicated; disabling; limiting self-care ADL**.	
Grade 4	Life-threatening consequences; urgent intervention indicated.	Note: Grade 4 and 5 adverse events should always be reported as serious adverse events
Grade 5	Death related to AE.	

Activities of Daily Living (ADL)

\* Instrumental ADLs refer to preparing meals, shopping for groceries or clothes, using the telephone, managing money, etc.

\*\*Self-care ADLs refer to bathing, dressing and undressing, feeding self, using the toilet, taking medications, and not bedridden.

The Investigator will suggest the relationship of an AE to the IP and will record it on the source documents and AE CRF, using the relationship categories defined in [Table 4](#) Description of Relationship to Adverse Event Categories.

**Table 4 Description of Relationship to Adverse Event Categories**

Relationship Category	Description
Not Related	
Exposure to the IP has not occurred
 
OR
 
The administration of the IP and the occurrence of the AE are not reasonably related in time
 
OR
 
The AE is considered likely to be related to an etiology other than the use of the IP; that is, there are no facts [evidence] or arguments to suggest a causal relationship to the IP.

Possibly Related	
The administration of the IP and the occurrence of the AE are reasonably related in time
 
AND
 
The AE could be explained equally well by factors or causes other than exposure to the IP.

Probably Related	
The administration of IP and the occurrence of the AE are reasonably related in time
 
AND
 
The AE is more likely explained by exposure to the IP than by other factors or causes.

In order to classify AEs and diseases, preferred terms will be assigned by the sponsor to the original terms entered in the CRF, using Medical Dictionary for Regulatory Activities (MedDRA) terminology.

## 11.2 Serious Adverse Events

A serious adverse event is any untoward medical occurrence that at any dose meets 1 or more of the following criteria:

- Is fatal
- Is life threatening
  - *Note: Life-threatening refers to an event that places the patient at immediate risk of death. This definition does not include a reaction that, had it occurred in a more severe form, might have caused death*
- Requires or prolongs in-patient hospitalization

	SMA-002	Page 33
---	---------	---------

- Results in persistent or significant disability or incapacity
- Is a congenital anomaly or birth defect, that is, an AE that occurs in the child or fetus of a patient exposed to IP prior to conception or during pregnancy
- Is an important medical event or reaction.

The reporting period for SAEs begins after informed consent is obtained for the current SMA-002 study and continues through 4 weeks after the last visit.

Any SAE, whether or not considered related to study drug, must be reported within 24 hours of knowledge of the event by forwarding (fax, email) the study-specific SAE Report Form to Catalyst and its designee PhAST Consulting s.r.l.. The Investigator should not wait to collect information that fully documents the SAE before notifying Catalyst. As additional information becomes available, including but not limited to the outcome of the SAE and any medication or other therapeutic measures used to treat the event, it must be reported within 24 hours in a follow-up report.

The Investigator should follow all unresolved SAEs until the events are resolved or stabilized, the patient is lost to follow-up, or it has been determined that the study treatment or participation is not the cause of the AE. Resolution of AEs (with dates) should be documented in the CRF and in the patient's medical record.

For some SAEs, Catalyst or designee may follow up by telephone, fax, email, and/or a monitoring visit to obtain additional case details deemed necessary to appropriately evaluate the SAE report (e.g. hospital discharge summary, consultant report, autopsy report).

At the last scheduled visit, the Investigator should instruct each patient to report any subsequent SAEs that the patient's personal physician(s) believes might be related to prior study treatment.

The Investigator should notify Catalyst and its designee PhAST Consulting s.r.l of any death or SAE occurring at any time after a patient has discontinued, or terminated study participation, if felt to be related to prior study treatment. Catalyst and its designee PhAST Consulting s.r.l should also be notified if the Investigator should become aware of the development of cancer, or of a congenital anomaly, in a subsequently conceived offspring of a patient that participated in this study.

Reporting of SAEs to the IEC will be done in compliance with the standard operating procedures and policies of the IEC and with applicable regulatory requirements. Adequate

	SMA-002	Page 34
---	---------	---------

documentation must be provided showing that the IEC was properly and promptly notified as required.

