**Table 1 Schedule of Events**

Study Assessment or Event	Screening and Enrollment*	End of Study Month ± 1 week							
		3	6	9	12	15	21	27	EoS g
Informed consent a	x								
Inclusion/Exclusion Criteria	x								
Complete physical exam b	x	x	x	x	x	x	x	x	x
Vital signs	x	x	x	x	x	x	x	x	x
12-Lead ECG	x	x	x	x	x	x	x	x	x
Clinical laboratory tests c	x	x	x	x	x	x	x	x	x
Pregnancy test d	x	x	x	x	x	x	x	x	x
Amifampridine Treatment		x	x	x	x	x	x	x	
QoL	x	x	x	x	x	x	x	x	x
Dispense IP e	x	x	x	x	x	x	x		
IP accountability		x	x	x	x	x	x	x	x
Adverse events/SAEs f	x	x	x	x	x	x	x	x	x
Concomitant medications	x	x	x	x	x	x	x	x	x

EoS= End of Study is the patients last visit to the site and discontinuation of study medication; IP=investigational product; QoL=quality of life; SAE=serious adverse event.

a Informed consent must be obtained before any study procedures are performed.

b Complete physical examination includes evaluation of all major body systems, including weight at all visits (Section 10.6.6).

c Clinical laboratory tests include serum chemistry, hematology, and urinalysis.

d Urine pregnancy tests will be obtained from female patients of childbearing potential.

e Pharmacist will dispense sufficient amount of medication until the next clinic visit. All unused medication must be returned to the clinic for drug accountability.

f SAE reporting commences after informed consent is signed. Non-serious adverse event reporting commences after the first dose of study drug for the current Long-Term Study.

g EoS or early termination visit if the last visit does not coincide the scheduled 3- or 6-month visit.

\*These data may be obtained from Study SMA-001. If data not available, then the assessment should be repeated.

	SMA-002	Page 20
---	---------	---------

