### 10.2.1 Inclusion Criteria

Individuals eligible to participate in this study must meet all the following inclusion criteria:

1. Participated in the SMA-001 study
2. Willing and able to provide written informed consent after the nature of the study has been explained and before the start of any research-related procedures.
3. Female patients of childbearing potential defined according to the Clinical Trial Facilitation Group - CTFG guidelines\* must have a negative pregnancy test (urine human chorionic gonadotropin [HCG] at the end of SMA-001 study); and must practice an effective, reliable contraceptive regimen during the study and for up to 30 days following discontinuation of treatment.
4. Ability to participate in the study based on overall health of the patient and disease prognosis, as applicable, in the opinion of the Investigator; and able to comply with all requirements of the protocol, including completion of study questionnaires.

\* According to CTFG guidelines a woman is considered of childbearing potential, i.e. fertile, following menarche and until becoming post-menopausal unless permanently sterile.

Permanent sterilisation methods include hysterectomy, bilateral salpingectomy and bilateral oophorectomy. A postmenopausal state is defined as no menses for 12 months without an alternative medical cause.

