#### **10.2.3 Removal of Patients from Treatment or Assessment**

Patients may withdraw their consent to participate in the study or to receive treatment with IP at any time without prejudice. The Investigator must withdraw from the study or from treatment with IP any patient who requests to be withdrawn. A patient's participation in the study or treatment with IP may be discontinued at any time at the discretion of the Investigator and in accordance with his or her clinical judgment.

Catalyst must be notified of all patient withdrawals from the study or from treatment with IP as soon as possible. Catalyst also reserves the right to discontinue the study at any time for either clinical or administrative reasons and to discontinue participation by an individual Investigator or site for poor enrollment or noncompliance.

Reasons for which the Investigator or Catalyst may withdraw a patient from the study treatment include, but are not limited to, the following:

- Patient experiences a serious or intolerable AE;
- Patient requires medication prohibited by the protocol;
- Patient becomes pregnant (refer to Section 11.4 for details on the reporting procedures to follow in the event of pregnancy);
- Patient does not adhere to study requirements specified in the protocol;
- Patient was erroneously admitted into the study or does not meet inclusion criteria;
- Patient is lost to follow-up.

If a patient fails to return for scheduled visits, a documented effort must be made to determine the reason. If the patient cannot be reached by telephone, a certified letter should

	SMA-002	Page 22
---	---------	---------

be sent to the patient requesting contact with the Investigator. This information should be recorded in the study records.

The Investigator or designee must explain to each patient, before enrollment into the study, that for evaluation of study results, the patient's protected health information obtained during the study may be shared with Catalyst, regulatory agencies, and IRB/IEC/REB. It is the Investigator's (or designee's) responsibility to obtain written permission to use protected health information, per country-specific regulations, from each patient. If permission to use protected health information is withdrawn, it is the Investigator's responsibility to obtain a written request, to ensure that no further data will be collected from the patient and the patient will be removed from the study.

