### 13.2 End of Months 3, 6, 9, 12, 15, 21 and 27 in Long Term Study

The following assessments and procedures will be determined at the end of Months 3, 6, 9, 12, 15, 21 and 27. Each month has a clinic visit window of  $\pm$  1 week. Additional visits are allowed as necessary.

- Assessment of AEs/SAEs;
- Complete physical exam with weight;
- Vital signs (seated position), including SBP, DBP, heart rate, respiration, and body temperature;
- Standard 12-lead ECG after 5 minutes in the supine position;
- Clinical laboratory tests including hematology, chemistry, and urinalysis;
- Urine pregnancy test in females of childbearing potential only;
- Concomitant medications;
- IP accountability of medication;
- QoL

	SMA-002	Page 37
---	---------	---------

All IP should be collected from the patient at each visit, in order to perform drug accountability. The investigator or her/his designee will dispense sufficient amifampridine for daily outpatient administration for 90 days (or 180 days from Months 15 to 27).

Patients may continue to receive amifampridine until the study is terminated, the patient decides to withdraw from the study, or the development program is discontinued for this indication.

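### For the 4 weeks after the last visit, Section 11.2 requires all-cause SAE reporting but has patients told to report SAEs a physician thinks related; the window also has no last-dose anchor

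*Protocol*

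**What the plan says.** Protocol Section 11.2 opens the SAE reporting period at SMA-002 consent, and the period "continues through 4 weeks after the last visit". Inside it the duty is all-cause: "Any SAE, whether or not considered related to study drug, must be reported within 24 hours of knowledge of the event". For the time after the last scheduled visit, the investigator is to instruct patients to report SAEs that the patient's "personal physician(s) believes might be related to prior study treatment". Section 11.2 also has the investigator notify the sponsor, with no time limit, of deaths and SAEs after participation ends if they are felt to be related to the study treatment.

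The Table 1 legend joins the last visit to the end of treatment: "EoS= End of Study is the patients last visit to the site and discontinuation of study medication". Footnote g makes the same column the early termination visit. Table 1 has no column after EoS. Section 10.1 allows telephone or video contact, but between the 3- or 6-month visits and if needed.

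Section 13.2 has drug dispensed for 90 days ("or 180 days from Months 15 to 27"). Section 10.2.3 foresees withdrawal at any time and lists "Patient is lost to follow-up" among the reasons for withdrawing a patient from treatment. If a patient does not return, it asks for a documented effort, by telephone and then by certified letter.

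**The concern.** There are two separate weaknesses.

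The first affects every patient on the planned path. For 4 weeks after the last visit the site owes the sponsor all SAEs, while the patient has been asked to pass on those that an outside physician links to the drug. The site's duty starts when it learns of the event. If it is told only of events thought to be related, it can follow the text exactly and still miss SAEs that the same section makes reportable.

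The second affects only patients who leave without an EoS or early termination visit. The window is counted from a visit, and the protocol does not say which visit that is for someone who stops attending. Such a patient may hold several months of drug.

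The Synopsis makes TEAE incidence, including SAEs, the primary endpoint. The SAP's definition of a TEAE (Section 10.12.1) starts at the first dose and has no stated end, so an SAE reported from this period would enter the treatment-emergent SAE (TESAE) tables. An SAE that the site never hears of would not.

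**Working it through.** The plan gives no figure of its own on this point. The check is a comparison of passages plus day arithmetic.

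**Patient instruction against reporting duty, in the 4 weeks after the last visit**

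- Reportable by the site: every SAE, related or not, once known (Section 11.2).
- What patients are asked to report: SAEs that a personal physician thinks might be related (Section 11.2).
- Scheduled contact through which the site would otherwise learn of events: none after EoS (Table 1).

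An SAE that the personal physician considers unrelated is inside required reporting, but no stated step brings it to the site. The failure is one of detection, not of scope.

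**Window against last dose**

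Inputs: a window of 4 weeks = 28 days after the last visit (Section 11.2); supply of 90 or 180 days (Section 13.2); EoS as both last visit and end of drug (Table 1).

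Coverage after the last dose = 28 + (day of last visit − day of last dose).

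- Last dose at the EoS visit: 28 + 0 = 28 days.
- Drug stopped 14, 30 or 90 days before the last visit (illustrative values): 28 + 14 = 42, 28 + 30 = 58, 28 + 90 = 118 days. Here the visit anchor lengthens coverage.

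Now take a patient with no EoS or early termination visit. Assume that the last visit means the last one attended and that dosing continues to the end of the dispensed supply.

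On-drug days outside the window = days of supply taken − 28.

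- 90-day supply: 90 − 28 = 62 days (62/90 = 69% of the supply period).
- 180-day supply: 180 − 28 = 152 days (152/180 = 84%).
- Drug stopped within 28 days of that visit: 0 days.

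The gap therefore ranges from 0 to 62 or from 0 to 152 days.

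**Effect on the tables**

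With about 12 patients (Synopsis), one patient whose only SAE is missed moves the TESAE row by 1/12 = 8.3 percentage points. The overall TEAE row moves by that amount only if the patient had no other TEAE.

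**A related inconsistency**

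Table 1 shows no dispensing at Month 27, while the wording of the 180-day supply in Section 13.2 runs to Month 27. These passages must be reconciled, because they determine whether a patient can hold study drug after the Month 27 visit.

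**The case against.** The strongest reply is that the written path has no on-drug gap. EoS is both the last visit and the end of drug, and it doubles as the early termination visit, so a patient who attends it has at least 28 days of all-cause reporting after the last dose. This stands. A reader might infer that SAEs on drug generally fall outside required reporting, or that this is so for all patients who drop out; the documents do not support either. The 62- and 152-day figures are ceilings that need all three assumptions, and the protocol nowhere says that the last visit means the last attended visit.

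It can also be said that the patient instruction does not contain the word only, does not tell patients to withhold other events and does not limit the investigator's duty. It resembles the open-ended duty to notify related events after participation, and so may be meant as an addition to the window. Following unresolved events to resolution can also bring contact after the visit, and the consent pages are not in the copy reviewed. All of this is fair. But the instruction takes effect at the last scheduled visit, when the 4 all-cause weeks begin, and nothing in Section 11.2 tells patients to report more broadly during them.

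A third reply is that for a patient who is lost the limit is knowledge, not window length. This stands in large part. Yet the telephone and letter effort in Section 10.2.3 may bring late news of an SAE. If that SAE began outside the window and is not felt to be related, Section 11.2 gives no clear duty to report it.

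Finally, one might set the 28 days against contraception "for up to 30 days following discontinuation of treatment" and call the two inconsistent. The periods serve different purposes and nothing requires them to match, so this comparison carries no weight.

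**Conclusion.** The point holds in a limited form and is worth a cheap correction. The mismatch between the patient instruction and the all-cause duty rests on the text alone and concerns the 4 weeks after the last visit. It puts detection at risk; it does not remove any SAE from required reporting.

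The missing last-dose anchor matters only for patients without an EoS or early termination visit. The exposure is 0 to 62 on-drug days with a 90-day supply and 0 to 152 with a 180-day supply, under the assumptions stated in the working. Related SAEs remain notifiable even then, if the investigator learns of them.

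A reader might infer a downward bias of 8 percentage points in the primary endpoint. The documents do not support that: they give no SAE rate and no loss rate, and the figure is what one missed patient would do to the TESAE row. Under-counting is possible, but its size is unknown.

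**What to change.** Amend Protocol Section 11.2 in two places.

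- **Patient instruction.** At the last scheduled visit, ask patients to report any SAE or hospitalisation, regardless of cause, during the 4-week window, and after it any SAE thought to be related to study treatment.
- **Window.** End it 4 weeks after the later of the last visit and the last known dose, and state how it is set for a patient without an EoS visit. That rule is needed, because if the last known dose falls at the last attended visit the window does not move. The date on which the last dispensed supply would run out is one workable default.

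Patients whose last dose is at or before an EoS visit see no change in window length. A patient who misses that visit and takes the whole supply gains the 62 or 152 on-drug days plus 28 days after the last dose.

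Optionally, add one closing telephone call at the end of the window, about 12 calls in all, to aid detection.

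The cost is a short amendment, a possible revision of the consent form with ethics committee approval (Section 15.7), and a few more SAE reports, mostly unrelated. The change will not capture events in patients who cannot be reached, or in those who withdraw permission to use their health information, for whom Section 10.2.3 stops further data collection.
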